8.7 Study size

For each database, all individuals that satisfy the eligibility criteria for a study cohort will be included.

8.8 Analysis

8.8.1 Descriptive statistics

The observed characteristics of each study population overall, and stratified by age, sex, prior COVID-19 diagnosis, prior SARS-CoV-2 vaccination, whether patients were hospitalised or whether patients were immunocompromised on their index date will be reported. The time at risk observed along with the number of events observed over follow-up will be summarised for each study population overall and by age and sex as well as stratified by whether individuals had a prior COVID-19 diagnosis, prior SARS-CoV-2 vaccination, where hospitalised on the index date or where immunocompromised on the index date. The proportion of missing data for a given characteristic, for example relating to smoking status, will also be reported.

8.8.2 Incidence of study outcomes

The incidence of each study outcome described in section 8.6.2 will be estimated during 30-, 60-, and 90- and 180-days following the index date for each cohort of interest with 95% confidence intervals in each database. The 90-day cumulative incidence of study outcomes will be estimated. Given the risk of mortality among patients with COVID-19, particularly among those hospitalised, the competing risk of mortality will be accounted for by estimating cumulative incidence functions. If death is not available, cumulative incidence will be estimated using the Kaplan-Meier approach. As well as estimating the incidence of outcomes for each study cohort as a whole, incidence will also be estimated by age group stratified by sex. Other stratifications by prior COVID-19 diagnosis, prior SARS-CoV-2 vaccination, whether patients were hospitalised on the index date or where immunocompromised on the index date will also be performed.

8.8.3 Assessing the association between risk factors for thromboembolic events and COVID-19 during the Omicron period

To assess the association between potential risk factors on the incidence of venous and arterial thromboembolic events among patients with COVID-19 during the Omicron period, cause-specific Cox models will be used to calculate hazard ratios for the incidence of venous and arterial thromboembolic events for each of the COVID-19 cohorts. Adjusted models will evaluate potential predictors including age, sex, prior COVID-19 infection status, prior vaccination status, cancer, whether patients were immunocompromised on the index date, prior use of antithrombotics, prior use of corticosteroids, and pre-index comorbidities listed in section 8.6.3.

8.8.4 Risks of COVID-19 “worsening” (hospital admission or death) stratified by thromboembolic event occurrence during the Omicron period

[This analysis will only be conducted in the SIDIAP data given the availability of hospital data]

A multistate-type modelling approach will be used to assess risks of COVID-19 worsening during the period when Omicron was the dominant variant, stratified by thromboembolic event occurrence. Multistate models allow for a consideration of individuals progression to multiple events of interest, extending on competing risk models by also describing transitions to intermediate events. [24] In the context of COVID-19, use of intensive care services during a hospitalisation can be considered as key intermediate events between testing positive for SARS-COV-2 or having a clinical diagnosis of COVID-19 in an outpatient setting on the one end to a COVID-19-related death on the other.

[figure not shown]
	Phase II C3-001 – Study Protocol	
	Author(s): [name], [name]	Version: v3.1
	Dissemination level: public	

Venous thromboembolism and arterial thromboembolism will be assessed separately, as time -dependent exposures for the following transitions:

- (1) from outpatient COVID-19 diagnosis or PCR test positive to hospitalised with COVID-19
- (2) from outpatient COVID-19 diagnosis or PCR test positive to death (without a COVID-19 hospitalisation in between)
- (3) from being hospitalised with COVID-19 to death

Figure 1 shows an exemplar model for assessing COVID-19 worsening stratified by venous thromboembolic event, where individuals would begin by being identified as having a positive test for SARS-CoV-2 or clinical diagnosis of COVID-19 in an outpatient setting and then would progress through the various hospitalisation-related states, and would capture deaths (either after such a hospitalisation or directly after the test, for those individuals who were not hospitalised before their deaths).

Figure 1. Example multi-state model framework to assess COVID-19 worsening stratified by venous thromboembolic event

Cause-specific Cox models within the multistate framework will be used to estimate hazard ratios associated with the risk factors of interest. This approach will allow for the factors of interest to have a different effect by the transition of interest and, where the model includes a state representing deaths, will account for the competing risk of mortality. Models will be adjusted for age and sex.

8.8.5 Contextualising incidence rates for thromboembolic events in COVID-19 during the period when Omicron was the dominant variant

	Phase II C3-001 – Study Protocol	
	Author(s): [name], [name]	Version: v3.1
		Dissemination level: public

We will calculate crude incidence rate ratios (IRRs) for each event with 95% confidence intervals, for the vaccinated and COVID-19 cohorts compared against the background general population cohort. This will be done both overall and stratified by key factors including age, sex, prior COVID-19 diagnosis, prior vaccination status and whether patients are immunosuppressed. We will estimate the number of events expected among the vaccinated and COVID-19 cohorts using indirect standardisation by age and sex (with 10-year age bands), using the general population cohort as the standard population. We will calculate standardized incidence rate ratios (SIRs) and 95% confidence intervals comparing observed and expected rates. Rates will be reported overall, and by 10-year age bands, by sex, by prior COVID-19 diagnosis, by prior vaccination status and whether patients were immunosuppressed. A standardized incidence rate ratio above 1 will indicate that the observed rate for a specific outcome is higher than what is expected in the general background population.

Table 8: Primary, secondary, and subgroup analysis specification

A. Primary analysis

Hypothesis:	Objective 1 -3: Not applicable, descriptive incidence rate. Objective 4: use of intensive care services during a hospitalisation can be considered as key intermediate events between testing positive for SARS-COV-2 or having a clinical diagnosis of COVID-19 in an outpatient setting on the one end to a COVID-19-related death on the other. Objective 5: Covid-19 infection or vaccination may change the incidence rate of study events in population.
Exposure contrast:	Objective 1 -3: Not applicable, descriptive incidence rate. Objective 4: Not applicable, risk factor analysis Objective 5: Infected or vaccinated vs. the non-infected or non-vaccinated population
Outcome:	Objective 1 -3: Incidence rates of VTE, ATE Objective 4: VTE, ATE, death Objective 5: Incidence rates of VTE, ATE
Analytic software:	R
Model(s): (provide details or code)	Objective 1 -3: We will use Poisson models to estimate incidence rates and 95% confidence interval. Overall, age group, and sex specific rates will be reported. Within each age-sex strata, rates by prior COVID-19 diagnosis, prior vaccination status and brand, and whether patients are immunosuppressed will be reported as well when event number is larger than 5 within the strata. Objective 4a: To assess the association between potential risk factors on the incidence of venous and arterial thromboembolic events among patients with COVID-19 during the Omicron period, cause-specific Cox models will be used to calculate hazard ratios for the incidence of venous and arterial thromboembolic events for each of the COVID-19 cohorts. Adjusted models will evaluate potential predictors including age, sex, prior COVID-19 infection status, prior vaccination status and brand, cancer, whether patients were immunocompromised on the index date, prior use of antithrombotics, prior use of corticosteroids, and pre-index comorbidities. Objective 4b: Cause-specific Cox models within the multistate framework will be used to estimate hazard ratios associated with the risk factors of interest. This approach will allow for the factors of interest to have a different effect by the transition of interest and, where the model includes a state representing deaths, will account for the competing risk of mortality. Models will be adjusted for age and sex. Objective 5: We will calculate crude incidence rate ratios (IRRs) for each event with 95% confidence intervals, for the vaccinated and COVID-19 cohorts compared against the background general population cohort. This will be

	Phase II C3-001 – Study Protocol	
	Author(s): [name], [name]	Version: v3.1
		Dissemination level: public

	done both overall and stratified by key factors including age, sex, prior COVID-19 diagnosis, prior vaccination status and brand, and whether patients are immunosuppressed. We will estimate the number of events expected among the vaccinated and COVID-19 cohorts using indirect standardisation by age and sex (with 10-year age bands), using the general population cohort as the standard population. We will calculate standardized incidence rate ratios (SIRs) and 95% confidence intervals comparing observed and expected rates. Rates will be reported overall, and by 10-year age bands, by sex, by prior COVID-19 diagnosis, by prior vaccination status and brand, and whether patients were immunosuppressed. A standardized incidence rate ratio above 1 will indicate that the observed rate for a specific outcome is higher than what is expected in the general background population.
Confounding adjustment method	Name method and provide relevant details, e.g. bivariate, multivariable, propensity score matching (specify matching algorithm ratio and caliper), propensity score weighting (specify weight formula, trimming, truncation), propensity score stratification (specify strata definition), other.
	For incidence rates, we will estimate the rates with stratification. For incidence rate ration, standardized incidence rate ratio (SIRs) will be calculated.
Missing data methods	Name method and provide relevant details, e.g. missing indicators, complete case, last value carried forward, multiple imputation (specify model/variables), other.
	For cohort 2-5, we will only include individuals with complete exposure information.
Subgroup Analyses	List all subgroups
	All analysis will be stratified by age, sex, prior COVID-19 diagnosis, prior SARS-CoV-2 vaccination, whether patients were hospitalised or whether patients were immunocompromised on their index date will be reported, when sample size allowed.

B. Secondary Analysis 1

The only difference between the primary and secondary analysis is the outcomes of interest. Hence here we only show this item in the table.

Outcome:	1. Venous thromboembolic events
-----------------	---------------------------------

	Phase II C3-001 – Study Protocol	
	Author(s): [name], [name]	Version: v3.1
	Dissemination level: public	

In a secondary analysis pulmonary embolism and deep vein thrombosis will be assessed separately. We will also assess portal vein thrombosis, splanchnic venous thrombosis (SVT) and cerebral venous sinus thrombosis separately.

2. Arterial thromboembolic events
In a secondary analysis acute myocardial infarction and acute ischemic stroke will be assessed separately. We also identify stroke in general, for which we will include both ischemic, haemorrhagic and non-specifically recorded stroke.

3. Cardiovascular events
Instances of heart failure, cardiac arrhythmia, and angina will be identified. In addition, major cardiovascular events (MACE) will be identified by heart failure, acute myocardial infarction, or stroke, or the occurrence of sudden cardiac death. As a sensitivity analysis, we will require that events were identified by hospitalisation admission or discharge records.

Table 9 Sensitivity analyses – rationale, strengths and limitations

	What is being varied? How?	Why? (What do you expect to learn?)	Strengths of the sensitivity analysis compared to the primary	Limitations of the sensitivity analysis compared to the primary
Restrict to RT-PCR test	In main analysis, the exposure definition of “Positive test result for SARS-CoV-2” will include all type of test. In the sensitivity analysis, we will restrict to RT-PCR test.	As a result of changes in the availability of population wide RT-PCR and home self-reported lateral flow tests during the Omicron period, it may not be possible to exclusively use RT-PCR tests when identifying positive test results in all datasets.	Increase specificity of exposure definition.	Loss in sensitivity.

	Phase II C3-001 – Study Protocol	
	Author(s): [name], [name]	Version: v3.1
		Dissemination level: public

Require inpatient cardiovascular events only	In the outcome definition of cardiovascular events, restrict to hospitalisation admission or discharge records	Cardiovascular events are acute and usually lead to inpatient admission	Increase specificity of exposure definition.	Loss in sensitivity.
Washout period for outcome events	In the main analysis, we will exclude patients with VTE or ATE within 183 days prior to the index date. Here, we will do 1.) reduce the period to 91 days. And 2.) exclude people with any VTE or ATE history	The choice of washout period may impact on the included study population, therefore impact on the generalisability of the rate for the vaccine cohort vs the risk of misclassification with prior event recording.	1.) can reduce the risk of survival bias; 2.) increase the specificity of incident event.	1.) may include recurrent events. 2.) increase the risk of survival bias as people need to have no VTE or ATE after prior vaccines to be included in the later vaccine cohorts.

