Studies assessing the incidence of thromboembolic events among people with COVID-19 during the early period of the pandemic were conducted in relatively small study populations, partly constrained by data availability at the time, and predominantly focused on hospitalised populations. Consequently, uncertainty remained around the incidence of thromboembolic events among patients with COVID-19. Several larger studies examining coagulopathy risk have since been conducted using routinely collected health data. One study from Sweden demonstrated an increased risk of deep vein thrombosis (DVT) up to 70 days post-COVID-19 diagnosis and an increased risk of pulmonary embolism up to 110 days post-COVID-19 diagnosis.[5] Meanwhile, another study from England reported an increased risk of venous thromboembolism up to 49 weeks post-COVID-19.[6] Studies have also observed that the elevated risk of thromboembolic events associated with COVID-19 infection may be attenuated following SARS-CoV-2 vaccination.[7] SARS-CoV-2 variants have changed over time, with Omicron now widely established as the dominant SARS-CoV-2 variant. On 26 November 2021, the European Centre for Disease Prevention and Control classified the Omicron B.1.1.529 variant as a variant of concern due to concerns regarding immune escape and potentially increased transmissibility compared to the SARS-CoV-2 delta variant.[8] However, existing studies largely examined COVID-19 during the period when Omicron was not the dominant variant. The risk of venous and arterial thromboembolic events with Omicron COVID-19 is therefore less well studied, particularly in the context of exposure to either prior COVID-19 infection or prior SARS-CoV-2 vaccinations.

Thromboembolic events and worsening of COVID-19 during the Omicron period

COVID-19 patients with thromboembolic events are at increased risk of worse outcomes, with a systematic review finding a strong association between cardiovascular and thromboembolic events and poor prognosis among people with COVID-19.[9] However, it has been suggested that the Omicron variant has a milder course and therefore, subsequent coagulopathy risk may differ. This may be further influenced by prior SARS-CoV-2 vaccination. As with measuring the incidence of thromboembolic events themselves, routinely collected data may also be used to describe the risks of worsening among people with COVID-19 during the period when Omicron was the dominant variant.

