8.3 Study Period

The study period will start depending upon when the Omicron variant became established in Europe commencing from 1st December 2021.[8] The end of the study period will be the last available date of data collection for each contributing dataset.

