8.4 Follow-up

For cohort 1, follow-up will begin on January 1st 2017 and continue up until the first of: outcome of interest, loss to follow-up, death or December 31st 2019. For cohorts 2 to 5, follow-up will begin on their index date and continue up until the first of: outcome of interest, end of observation period, end of data availability, death, or either 30-, 60-, 90- or 180-days after the index date (depending upon the follow-up time period of interest).

Table 2: Operational Definition of Time 0 (index date) and other primary time anchors

Study population name(s)	Time Anchor Description (e.g. time 0)	Number of entries	Type of entry	Washout window	Care Setting ¹	Code Type	Diagnosis position	Incident with respect to...	Measurement characteristics / validation	Source of algorithm
Background population (cohort 1*)	January 1 st 2017 or after when they have 365 days of prior history	Multiple	General population	n/a	n/a	n/a	n/a	n/a	n/a	n/a
SARS-CoV-2 infection cohort (cohort 2*)	Date of test for the positive test result for SARS-CoV-2, or date of clinical diagnosis of COVID-19	Multiple	incident	No covid-19 infection within 3 months prior	OP	SNOMED codes (see appendix)				
hospitalised with COVID-19 cohort (cohort 3*)	Date the date of hospital admission	Multiple	incident	No hospitalization within	IP	SNOMED codes (see appendix)				

This document represents the views of the DARWIN EU® Coordination Centre only and cannot be interpreted as reflecting those of the European Medicines Agency or the European Medicines Regulatory Network.

	Phase II C3-001 – Study Protocol	
	Author(s): [name], [name]	Version: v3.1
	Dissemination level: public	

				3 month s prior						
Intensive care service cohort (cohort 4*)	Date of the following depends on availability in data, descend priority: 1.)Date of intensive care service (mechanical ventilation, tracheostomy, or extracorporeal membrane oxygenation (ECMO)); 2.)Date of ICU admission; 3.)Date of hospital admission.	Multiple	incident	n/a	IP	SNOMED (see appendix)	n/a	Covid-19 hospitalized	n/a	n/a
Vaccinated cohort (cohort 5*)	date of vaccination record	Multiple	n/a	21 days	OP	RxNorm codes (see appendix)				

*Cohorts number as described in 8.5 study population with inclusion and exclusion criteria.

¹ IP = inpatient, OP = outpatient, ED = emergency department, OT = other, n/a = not applicable

Description of the different items from the table can be found below:

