8.5 Study Population with inclusion and exclusion criteria

Five non-mutually exclusive study cohorts for the analyses will be defined:

- 1. General population cohort for pre-pandemic background rates** will have
 - Individuals will start contributing as of 1st January 2017, or when they have at least 365 days of data availability.
 - follow-up for this cohort will run up to 31 December 2019.
- 2. Persons tested positive for SARS-CoV-2 or with a clinical diagnosis of COVID-19 during the Omicron period** will
 - have either a positive test result for SARS-CoV-2 or a clinical diagnosis of COVID-19 on or after 1st December 2021 (with the index date being whichever date comes first if both occur)
 - have no positive test result for SARS-CoV-2 or clinical diagnosis of COVID-19 within 3 months prior to the index date.
 - have at least 365 days of data availability prior to index date
- 3. Persons hospitalised with COVID-19 during the Omicron period** will have
 - a hospitalisation on or after 1st December 2021 (with the index date the date of hospital admission),
 - a record of a clinical diagnosis of COVID-19 or a positive test result for SARS-CoV-2 in the period between 3 weeks prior to and up to 3 days following the index date.
 - have no diagnosis of COVID-19 or a positive test result for SARS-CoV-2 between 3 months and 3 weeks prior to index date.
 - have no COVID-19 hospitalisation within 3 weeks prior to the index date.
 - have at least 365 days of data availability prior to index date
- 4. Persons requiring intensive services during a hospitalisation with COVID-19 during the Omicron period** will have
 - intensive services initiated during a hospitalisation as described in cohort 3 (with the index date the date at which intensive services were initiated)
 - patients will have had a confirmatory diagnosis or test result of COVID-19 (both as defined above) within a time window from 3 weeks to their index date up to three days following their index date.
 - have at least 365 days of data availability prior to index date
- 5. Persons vaccinated against SARS-CoV2 infection**
 - a vaccination record identified by brand (with the index date the date of vaccination record)

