8.9 Evidence synthesis

We will pool the results across databases using random effect meta-analyses, I^2 for heterogeneity will be reported.

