The included databases will vary in the data elements that they capture and in their current duration of follow-up. Depending on the dataset, not all study populations will be observed. For example, identifying the intensive services cohort will not be possible where inpatient hospital interventions are not observed. Similarly, not all outcomes may be available in all databases e.g. deaths. Some datasets may not capture COVID-19 diagnoses or tests occurring outside of hospital. Only the cohorts and outcomes that can reliably be identified will be assessed in the analyses. Since the vaccination programs changed over time (e.g. the primary vaccine courses targeted the general population, while the 4th dose were offered to more vulnerable people), the characteristics of patients receiving different doses may differ. However, we will stratify our analysis by prior vaccines whenever the power allows. It will also be assumed that vaccination recording is complete. Due to the availability of more recent data (CPRD is available until July 2022), some databases may have relative short follow-up time for study cohorts, and therefore may impact on the 90-days and 180-days incidence rates. The data elements that each data partner can provide will be detailed. The contextualisation of incidence rates using a historical background period assumes that coding practices and data recording are similar over time. However, this method has been used in previous studies focused on the 1st wave of covid, conducted by the same research group. [20,21] The analysis will calculate crude incidence rates and standardised incidence rates accounting for age and sex only. Differences in other potential confounders factors may exist and the characteristics of each cohort and stratification group will be inspected. No validation of outcomes using case note review will be performed.

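### COVID-19 cohorts: the cumulative 180-day rates and SIRs rest on a different mix of early and late follow-up in each database, most severely in SIDIAP, and are then pooled

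*Protocol*

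**What the plan says.** Section 8.5 admits to cohort 2 people who "have either a positive test result for SARS-CoV-2 or a clinical diagnosis of COVID-19 on or after 1st December 2021". Cohorts 3 and 4 use the same start date for the hospitalisation. No last index date is given. Section 8.3 closes the study by database: "The end of the study period will be the last available date of data collection for each contributing dataset". Section 8.7 sets no minimum follow-up: "all individuals that satisfy the eligibility criteria for a study cohort will be included".

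Section 8.4 ends follow-up at the first of the outcome, "end of observation period, end of data availability, death, or either 30-, 60-, 90- or 180-days after the index date". Every window therefore starts at the index date and is cumulative, and the lock can cut any of them short. Section 8.8.2 asks for all four windows in each database ("The incidence of each study outcome described in section 8.6.2 will be estimated during 30-, 60-, and 90- and 180-days following the index date"), and Table 8 estimates the rates with Poisson models. Section 8.8.5 turns them into SIRs against the background cohort. Section 8.9 adds: "We will pool the results across databases using random effect meta-analyses", with I² reported.

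Table 1 gives the locks: SIDIAP 1/6/2022, CPRD GOLD 07/2022, IQVIA Germany 1/9/2022, IPCI 1/12/2022. The Setting row of the objectives table in section 7 states that only SIDIAP has inpatient data.

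Section 11 concedes that "some databases may have relative short follow-up time for study cohorts, and therefore may impact on the 90-days and 180-days incidence rates". It gives CPRD as the example and changes nothing in the analysis. Cumulative incidence that allows for censoring is planned at 90 days only (section 8.8.2).

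**The concern.** A person-time rate over 0 to 180 days is an average of the hazard, weighted by how many people are still observed on each day. If many are cut off by the lock, the early days get more weight than the label implies. That is harmless when the hazard is flat. It matters when the hazard is highest soon after infection, and section 6 gives reason to expect this: "One study from Sweden demonstrated an increased risk of deep vein thrombosis (DVT) up to 70 days post-COVID-19 diagnosis", and up to 110 days for pulmonary embolism in the same study.

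The SIR does not cancel the effect. Expected events apply a background rate to the same truncated person-time, so within an age-sex stratum observed over expected rises by the same factor as the rate.

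The locks span six months, so the factor differs by database for calendar reasons alone. The meta-analysis would then combine different quantities and report the difference as between-database heterogeneity. For the hospitalised and intensive-care cohorts no second database exists to show the problem.

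**Working it through.** The protocol states no expected follow-up, so there is no figure of its own to reproduce. The check uses its dates plus labelled assumptions.

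**Step 1: dates.** D is the number of days from 1 December 2021 to the lock. The last index date with a full 180 days is the lock minus 180 days. If entry were uniform over calendar days, the share completing 180 days is (D − 180 + 1)/(D + 1). CPRD's day is not given, so both ends of July are shown.

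| Database | D | Last index date for 180 days | Share completing, uniform entry |
|---|---|---|---|
| SIDIAP | 182 | 3 Dec 2021 | 3/183 = 1.6% |
| CPRD, 1 or 31 July | 212 or 242 | 2 Jan or 1 Feb 2022 | 33/213 = 16% or 63/243 = 26% |
| IQVIA Germany | 274 | 5 Mar 2022 | 95/275 = 35% |
| IPCI | 365 | 4 Jun 2022 | 186/366 = 51% |

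The SIDIAP date limit does not depend on the shape of the wave. Under the front-loaded and peaked entry patterns tried, the SIDIAP share was 0.8% to 9.5%.

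**Step 2: size.** Neither the entry pattern nor the hazard shape is in the protocol, so both are assumed and varied. The hazard is h times baseline for 30 days, then baseline, with h from 2 to 10. F is potential follow-up to the lock. Only administrative censoring is modelled.

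Ratio of the truncated to the complete 180-day rate = {[(h − 1)·E min(F,30) + E min(F,180)] / E min(F,180)} ÷ {[30h + 150]/180}

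Under uniform entry, E min(F,w) = w − w²/(2D). For SIDIAP:
- E min(F,30) = 30 − 900/364 = 27.53
- E min(F,180) = 180 − 32400/364 = 90.99
- h = 2: (27.53 + 90.99)/90.99 = 1.303; divided by 210/180 = 1.167, this gives 1.12
- h = 10: (9 × 27.53 + 90.99)/90.99 = 3.723; divided by 450/180 = 2.5, this gives 1.49

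For front-loaded entry, the entry density is proportional to exp(−e/m) on 0 to D, with m = 60 or 30 days and F = D − e. The expectations were integrated numerically. For SIDIAP with m = 60 they are 29.55 and 131.17, giving 1.05 (h = 2) and 1.21 (h = 10).

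| Overstatement of 180-day rate, h = 2 to 10 | Uniform | Mean 60 days | Mean 30 days |
|---|---|---|---|
| SIDIAP | 12-49% | 5-21% | 3-11% |
| CPRD (1 July lock) | 9-37% | 3-11% | 1-4% |
| IQVIA Germany | 6-24% | 1-3% | under 0.5% |
| IPCI | 4-16% | under 1% | under 0.5% |

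A 31 July lock for CPRD lowers its uniform range to 7-30%. With h = 1 the ratio is 1 everywhere.

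**Step 3: 90 days.** Replacing 180 by 90 in the same formula, uniform entry gives 5-16% in SIDIAP and 2-7% in IPCI. With mean-60-day entry, SIDIAP falls to 1-4%. Completion of 90 days under uniform entry is 51% (SIDIAP) to 76% (IPCI).

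**The case against.** **The bias needs a falling hazard.** This stands. Section 6 also cites raised venous thromboembolism risk up to 49 weeks in England; an elevation constant through day 180 would give no bias. The 30-day step matches neither cited study. Raising the hazard for 110 days instead, uniform entry and h = 10 give about 32%, 24%, 16% and 11% (SIDIAP, CPRD at 1 July, IQVIA Germany, IPCI) instead of 49%, 37%, 24% and 16%. The SIDIAP figure for h = 2 rises from 12% to 14%.

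**Entry was probably not uniform.** This stands as a caution on size. If infections came early, the effect is about 3% or less in IQVIA Germany and IPCI. The gap between SIDIAP and IPCI remains in every pattern tried.

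**The limitation is disclosed, and results appear by database with time at risk and I².** This stands in part. Section 11, however, names CPRD although SIDIAP locks earlier. Its rule to assess only what can be reliably identified covers cohorts and outcomes, not windows.

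**The locks may move.** Table 1 lists the lock of the latest update, and code execution is still to be confirmed in section 5. A later extract would shrink the problem. Section 11 does treat CPRD's July 2022 date as current.

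**Interval displays belong in an SAP.** The display could be placed there. But the protocol itself fixes the windows, estimator, censoring and pooling, and that combination creates the problem.

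**Conclusion.** The point holds for the cumulative 180-day rates and SIRs of cohorts 2 to 4. It is certain as to dates: at the stated lock SIDIAP has three index days that can complete 180 days. It is conditional as to bias: overstatement requires a hazard that declines after infection, and its size depends on the entry pattern. Under the assumptions shown, SIDIAP is overstated by about 3% to 49%, and the other databases by less under each pattern.

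A reader might infer four stronger things that the document does not support:
- **That the 90-day results fail equally.** The effect there is smaller, and the planned 90-day cumulative incidence already handles administrative censoring.
- **That the vaccinated cohort is affected in the same way.** The abstract allows vaccinations outside the Omicron period and cohort 5 has no December 2021 start, so earlier doses can complete 180 days. Whether the study-period start in section 8.3 applies to them is unclear.
- **That every database yields only an early-time rate.** Under uniform entry, days 90 to 179 still supply 32-42% of the 180-day person-time outside SIDIAP, against 50% if complete and 26% in SIDIAP.
- **That overstatement is inevitable.** A constant hazard gives none.

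The change is worth making before the code is written, but the flaw does not undermine the study as a whole.

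**What to change.** - **Sections 8.8.2 and 8.8.5:** for the COVID-19 cohorts, report rates and SIRs in disjoint intervals (0-30, 31-60, 61-90, 91-180 days) alongside the cumulative windows, and pool by interval. This largely removes the mixture problem and keeps every participant.
- **Section 8.9:** do not pool or headline a cumulative 180-day COVID-19 rate or SIR from a database whose lock leaves almost nobody with 180 days of potential follow-up, as in SIDIAP at the stated lock. Tie the rule to the lock actually used, so that a later extract is treated correctly.
- **Section 11:** name SIDIAP as the most affected database.

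An index-date restriction on the cumulative windows should not be required. At the stated lock it would leave SIDIAP three days of entrants, exchanging truncation for calendar selection.

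The cost is analysis code and more output, with wider confidence intervals for days 91-180. Section 5 still lists code creation as to be confirmed.
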